8.1 Definitions

Unanticipated Problems Involving Risk to Subjects or Others

Any incident, experience, or outcome that meets all of the following criteria:

- Unexpected in nature, severity, or frequency (i.e. not described in study-related documents such as the Institutional Review Board (IRB)-approved protocol or consent form, the investigators brochure, etc.)
- Related or possibly related to participation in the research (i.e. possibly related means there is a reasonable possibility that the incident experience, or outcome may have been caused by the procedures involved in the research)
- Suggests that the research places subjects or others at greater risk of harm (including physical, psychological, economic, or social harm).

Adverse Event

An **adverse event** (AE) is any symptom, sign, illness or experience that develops or worsens in severity during the course of the study. Intercurrent illnesses or injuries should be regarded as AEs. Abnormal results of diagnostic procedures are considered to be AEs if the abnormality:

- results in study withdrawal
- is associated with an SAE
- is associated with clinical signs or symptoms
- leads to additional treatment or to further diagnostic tests
- is considered by the investigator to be of clinical significance

A pre-existing condition should be recorded as an AE if the frequency, intensity or the character of the condition changes.

Serious Adverse Event (SAE)

Adverse events (AEs) are classified as serious or non-serious. An **SAE** is any AE that, in the view of either the investigator or the sponsor, is:

- fatal
- life-threatening
- requires or prolongs hospital stay

CONFIDENTIAL

- results in persistent or significant disability or incapacity
- a congenital anomaly or birth defect
- an important medical event

Important medical events are those that may not be immediately life threatening, but are clearly of major clinical significance. They may jeopardize the subject, and may require intervention to prevent one of the other serious outcomes noted above. For example, drug overdose or abuse, a seizure that did not result in in-patient hospitalization or intensive treatment of bronchospasm in an emergency department would typically be considered serious.

All AEs that do not meet any of the criteria for serious should be regarded as *non-serious adverse events*.

Unanticipated Adverse Device Effect (UADE)

A UADE is any serious adverse effect on health or safety, or any life-threatening problem or death caused by, or associated with, a device, if that effect, problem, or death was not previously identified in nature, severity, or degree of incidence in the investigational plan or application, or any other unanticipated serious problem associated with a device that relates to the rights, safety, or welfare of subjects.

Preexisting Condition

A preexisting condition is one that is present at the start of the study. A preexisting condition should be recorded as an AE if the frequency, intensity, or the character of the condition worsens during the study period.

General Physical Examination Findings

At screening, any clinically significant abnormality should be recorded as a preexisting condition. At the end of the study, any new clinically significant findings/abnormalities that meet the definition of an AE must also be recorded and documented as an AE.

Post-study Adverse Event

All unresolved AEs are followed by the investigator until the events are resolved, the subject is lost to follow-up, or the AE is otherwise explained. At the last scheduled visit, the investigator should instruct each subject to report any subsequent event(s) that the subject, or the subject's personal physician, believes might reasonably be related to participation in this study.

Hospitalization, Prolonged Hospitalization or Surgery

Any AE that results in hospitalization or prolonged hospitalization is documented and reported as an SAE unless specifically instructed otherwise in this protocol. Any condition responsible for surgery should be documented as an AE if the condition meets the criteria for an AE.

CONFIDENTIAL

This material is the property of the University of Pennsylvania.

Neither the condition, hospitalization, prolonged hospitalization, nor surgery are reported as an AE in the following circumstances:

- Hospitalization or prolonged hospitalization for diagnostic or elective surgical procedures for a preexisting condition. Surgery should **not** be reported as an outcome of an AE if the purpose of the surgery was elective or diagnostic and the outcome was uneventful.
- Hospitalization or prolonged hospitalization required to allow efficacy measurement for the study.
- Hospitalization or prolonged hospitalization for therapy of the target disease of the study, unless it is a worsening or increase in frequency of hospital admissions as judged by the clinical investigator.

8.2 Expected Adverse Events and Treatment

For all expected AEs, the treatment decisions would be to watchful wait, slow the rate of infusion or discontinue infusion, as appropriate.

Anaphylactic or Urticarial Reactions

Anaphylactic or urticarial reactions have been reported in patients with or without history of allergy to iodides. If such reactions occur, treatment with the appropriate agents (e.g., epinephrine, antihistamines, and corticosteroids) should be administered.

Hypertension

Infusion of indocyanine green may need to be stopped if patient becomes symptomatic at any level or, in the asymptomatic elevation of diastolic BP to ≥ 100 or systolic BP ≥ 200 . The PI/APP are notified when the BP elevations are reaching levels of concern.

Mild Arm Discomfort/Pain

If patients experience any arm/shoulder pain or discomfort at the IV site, the nursing staff are instructed to apply a hot pack or compress at the area of pain.
Infusion of indocyanine green may need to be stopped if patient cannot handle pain or pain has not subsided.

General Disorders

If subjects become symptomatic (fatigue, headache, fever-like symptoms, itching, etc), the PI/APP would be consulted for treatment and infusion decisions.

Administration Site Conditions

If subjects experience tenderness or muscle spasms during the infusion, the nursing staff evaluates as necessary and provides hot pack/compress to the IV site. If subjects experience extravasation of the drug, the infusion may be changed to the other arm or discontinued.

Gastrointestinal Disorders

If subjects become nauseous during the infusion, the infusion is discontinued.

CONFIDENTIAL

Impact of Indocyanine Green on Pulse Oximetry Readings

A slight decrease of pulse oximetry readings is expected. To date, no treatment has been necessary, as pulse oximetry readings return to normal following completion of infusion.

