1.7 Risk/Benefit Assessment

1.7.1 Known Potential Risks

Risks of Indocyanine Green:

The risks of using indocyanine green are well described and exceedingly rare [15, 28]. Indocyanine green is known to have a rare but serious side effect known as anaphylaxis and because of this, patients with a history of iodide allergies will not be considered candidates in this study. There is no connection with any other particular contrast agent or drug or food allergy. Anaphylaxis is an allergic reaction to a substance that can cause swelling of the skin, shortness of breath, dizziness, increased heart rate (HR), rash, and/or death. The indocyanine green dye will be administered in a procedure room with trained nurses who will closely monitor the subject's vital signs (HR, blood pressure [BP], oxygen level [pulse oximetry], and skin color) to check for any signs of anaphylaxis. In the event of an anaphylactic reaction, the indocyanine green injection will be stopped and medication will be used to control the reaction. One study placed the rate of adverse reactions for indocyanine green injections at fewer than 4 in 240,000 [29].

Adverse Events (as of January 2019):

The AEs table below outlines the number of events that occurred by Common Terminology Criteria for Adverse Events (CTCAE) v4.0 event category in this protocol as of January 2019. Subjects could have had more than one AE. Of 296 infusions, there were 55 total AEs observed in 35 patients: 36 events in the 5 mg/kg dose cohort and 19 events in the 2.5 mg/kg dose cohort. Out of the 55 AEs, one was a serious adverse event (SAE) (HTN). One patient experienced two unique AEs during infusion (HTN-General Disorder).

Overall, in 296 patients, HTN accounted for 5.7% of AEs; mild arm pain/discomfort accounted for 7.4% of AEs, general disorders accounted for 2.7%, administration site conditions accounted for 2% of AEs and 0.6% patients reported a gastrointestinal issue.

Of the patients in the **5 mg/kg dose cohort**, 5.4% reported vascular disorders, 9.1% reported mild arm discomfort or pain, 3.2% had general disorders and 1.6% had administration site conditions.

Of the patients in the **2.5 mg/kg dose cohort**, 6.4% reported vascular AEs, 4.6% of them had mild arm discomfort or pain, 1.8% had general disorders, 2.7% had administration site conditions and 1.8% had gastrointestinal AEs.

CONFIDENTIAL

This material is the property of the University of Pennsylvania.

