6.2 Visit 2 (CTRC, Infusion visit within 72 hours before operation)

For subjects receiving ICG with 72 hours of surgery, they will arrive at the Perelman Center for Advanced Medicine Clinical & Translational Research Center, [name] or the ACC, Farm Journal Building at PAH, [name], or the ACC at PPMC, [name] for their infusions at their respective infusion locations within 72 hours prior to the scheduled surgery to receive their injection of indocyanine green by trained nursing staff. The nursing staff places a peripheral IV and calls the pharmacy for the scheduled infusion of up to 5 mg/kg of indocyanine green diluted in sterile water administered intravenously in the dark, over 40 minutes. The nurse monitors subjects pre infusion, during the 40-minute infusion and for 30 minutes post infusion for any signs of anaphylaxis. For all AEs and prescribed treatment, please see **Section 6.5** and **8.2** Expected Adverse Events and Treatment).

During the study visit, subjects' vital signs are monitored as follows: pre infusion; then at 5 minutes after infusion starts, then at every 15 minutes over the 40-60 minute infusion time frame. During the post infusion 30 minute observation period, vital signs are completed at 10-minute intervals and the subject is monitored for any signs of anaphylaxis. The following vital signs are monitored and recorded during each time point: HR, BP, skin color, and oxygen levels (pulse oximetry) and the subject is observed for any adverse sign or symptoms that could include but is not limited to HTN, mild pain or discomfort at infusion site and signs of anaphylaxis. Symptoms are treated according to prescribed interventions outlined in the ICG Treatment Plan.

The Neurosurgeon may want to compare both indocyanine green with other Standard of Care NIR dyes (ex: 5-ALA) intra-operatively to see which dye localizes more accurately and precisely at the region of interest. This may result in using more than one dye for your surgery.

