6.5 Rescue Therapy

There is a possibility of anaphylaxis in patients with iodide allergies and these patients are not considered candidates in this study. Anaphylaxis is a reversible condition when treated quickly, and our subject population is monitored at the time of injection (see [Section 8.2](#)).

7 Statistical Plan

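### Stopping for anaphylaxis is mandatory in section 1.7.1 but discretionary in section 8.2, the section that staff are sent to

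*Combined protocol and SAP*

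**What the plan says.** Section 1.7.1 (Known Potential Risks) describes anaphylaxis as rare but serious, names death among its possible consequences, and commits to an action: "In the event of an anaphylactic reaction, the indocyanine green injection will be stopped and medication will be used to control the reaction".

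Section 8.2 (Expected Adverse Events and Treatment) begins with a rule for the whole list: "For all expected AEs, the treatment decisions would be to watchful wait, slow the rate of infusion or discontinue infusion, as appropriate". The first event listed is anaphylactic or urticarial reactions, and the instruction there is: "If such reactions occur, treatment with the appropriate agents (e.g., epinephrine, antihistamines, and corticosteroids) should be administered". That paragraph does not mention the infusion.

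Other paragraphs of 8.2 do mention it. For hypertension: "Infusion of indocyanine green may need to be stopped if patient becomes symptomatic at any level". For nausea: "If subjects become nauseous during the infusion, the infusion is discontinued".

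Three sections lead to 8.2. Section 5.1.2 (Treatment Regimen) names it for any adverse event. Section 6.2 (the infusion visit) names 6.5 and 8.2. Section 6.5 (Rescue Therapy) refers back to 8.2. Section 6.2 also names another source: "Symptoms are treated according to prescribed interventions outlined in the ICG Treatment Plan". No item under that title appears in the section 15 list of attachments.

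**The concern.** One reaction has a binding instruction in one section and a menu of options in another. The binding text sits in the introduction, outside the chain of references that staff are told to follow. A nurse or anesthesiologist who consults 8.2 alone cannot learn from it that 1.7.1 requires a stop.

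This is first a patient-safety matter, because the protocol itself says the reaction can be fatal. It also affects oversight. Section 10.3 requires departures from the protocol to be identified and documented. If an infusion were slowed, not stopped, during an anaphylactic reaction, the action would depart from 1.7.1 yet fall within the options in the opening sentence of 8.2. An auditor could not say from the text whether the protocol had been followed.

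**Working it through.** No figure in the plan bears on this point and no arithmetic applies. The check is a comparison of the texts.

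**Step 1. Are the two sections about the same event and the same act?** Section 1.7.1 speaks of the injection and 8.2 of the infusion, but section 6.2 uses both words for the same pre-operative administration, so the difference in terms does not separate the rules. Section 8.2 lists the reaction under its own subheading, so the opening sentence on all expected events covers it.

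**Step 2. What does each text say about stopping?**

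| Text | Instruction on the infusion | Force |
|---|---|---|
| 1.7.1, anaphylaxis | Stop, and medicate | Mandatory |
| 8.2, opening sentence, all expected events | Wait, slow or discontinue | Discretionary |
| 8.2, anaphylactic or urticarial reactions | None; drug treatment only | Falls back on the opening sentence |
| 8.2, hypertension | Possible stop, on symptoms or blood-pressure limits | Conditional |
| 8.2, arm pain | Possible stop if pain is not tolerated or persists | Conditional |
| 8.2, general disorders | Consult on infusion decisions | Discretionary |
| 8.2, extravasation | Change arm or discontinue | Discretionary |
| 8.2, nausea | Discontinue | Mandatory |

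**Step 3. Is silence about the infusion simply the style of 8.2?** No. The hypertension, arm-pain, general-disorder, extravasation and nausea paragraphs all address the infusion. The anaphylaxis paragraph carries over the medication half of the commitment in 1.7.1 and leaves out the stop. Read literally, 8.2 binds staff to stop for nausea but not for anaphylaxis.

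**Step 4. Does 8.2 agree with itself?** Not fully. The opening sentence offers three options for all expected events, while the nausea paragraph allows one. The section does not say whether its specific paragraphs override the general sentence.

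**Step 5. Do the references lead a reader to the mandatory text?** Section 5.1.2 leads to 8.2, section 6.2 to 6.5 and 8.2, and section 6.5 to 8.2. None leads to 1.7.1.

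**Step 6. Is the stop stated elsewhere?** Section 4.7.1 lists a serious event, or an event during injection that needs steroids or epinephrine, as a possible reason for a subject to be non-evaluable. That concerns the subject's place in the study and is not an instruction about the infusion. The ICG Treatment Plan is not reproduced, and part of section 1.7.1 was not in the text available, so neither could be checked.

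**The case against.** The best defence is that the sections can be followed together. Discontinuation is one of the three options in 8.2, drug treatment is in both sections, and a team that stops and medicates satisfies each. The words about acting as appropriate leave room for a trained nurse to stop, and a general sentence followed by specific paragraphs is a normal way to write such a section. Much of this stands: the rules are not mutually exclusive, and a reader who infers that 8.2 forbids or lacks any stop for anaphylaxis goes too far. Nor is it right that every expected event may be waited out, because nausea has its own rule.

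The defence does not close the gap. Letting the specific paragraph prevail settles nausea, but it cannot settle anaphylaxis, where the specific paragraph is silent and only the discretionary sentence remains. Permission to stop is not the requirement that 1.7.1 states.

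Two further readings are tempting and are not supported.

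- Section 6.5 might seem to confine anaphylaxis to excluded patients: "There is a possibility of anaphylaxis in patients with iodide allergies and these patients are not considered candidates in this study". Section 8.2 says: "Anaphylactic or urticarial reactions have been reported in patients with or without history of allergy to iodides". But 6.5 does not say that only those patients react. Its next sentence relies on monitoring the enrolled subjects, so the two can be read together.
- The ICG Treatment Plan might seem to be a third, conflicting rule. Its content is unknown. It could repeat the stop, form part of a listed attachment, or be another name for 8.2. All that can be said is that the reference is unresolved.

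**Conclusion.** The point holds as an inconsistency of force and an omission. Section 1.7.1 requires the injection to be stopped for anaphylaxis. Section 8.2 leaves that to discretion, and its anaphylaxis paragraph does not mention it. A smaller mismatch lies within 8.2, between the opening sentence and the nausea paragraph. It should be corrected because it concerns the handling of a reaction that the protocol says can cause death.

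The finding is textual and has no numerical size. The adverse-event percentages in 1.7.1 cover other categories, and neither they nor a bound on the anaphylaxis rate would measure a disagreement between two instructions.

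A reader might also infer that inconsistent stopping makes the dose data incomparable between staff or hospitals. The documents do not support this. They give no count of stopped or slowed infusions. Section 8.3 records the action taken for each event, so changes to an infusion made because of an adverse event should be identifiable. Under section 4.7.1, subjects who needed steroids or epinephrine may be non-evaluable.

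The conclusion rests on the protocol text as read. If the ICG Treatment Plan states the stop, the practical risk is smaller, but sections 1.7.1 and 8.2 would still differ.

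**What to change.** - Reconcile sections 1.7.1 and 8.2 so that the operational section states one consistent rule on the infusion for anaphylactic or urticarial reactions. Make clear whether both kinds of reaction fall under it, since the stop in 1.7.1 is worded for anaphylaxis while 8.2 treats the two together.
- State in 8.2 how its opening sentence relates to the event-specific paragraphs, so that the status of the nausea rule and of each other paragraph is plain.
- Resolve the reference in 6.2: identify the ICG Treatment Plan and where it is held, or name the protocol section that is meant.

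Which clinical rule applies is for the investigators to decide. The cost is a wording amendment to 8.2 and 6.2, to 1.7.1 if needed, and a short re-brief of the staff who give the dye. No procedures, visits or subjects are added.

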8.3 Recording of Adverse Events

Safety is assessed by monitoring and recording potential adverse effects using the CTCAE Version 4.0 at each study visit. Participants are monitored by medical histories, physical examinations, and other studies. If CTCAE grading does not exist for an AE, the severity of mild, moderate, severe, life-threatening, and death, corresponding to Grades 1-5, is used whenever possible.

At each contact with the subject, the investigator must seek information on AEs by non-directive questioning and, as appropriate, by examination. Adverse events may also be detected when they are volunteered by the subject during the screening process or between visits, or through physical examination, laboratory test, or other assessments. Information on all AEs should be recorded immediately in the source document, and also in the appropriate AE module of the case report form (CRF). All clearly related signs, symptoms, and abnormal diagnostic procedures results are recorded in the source document, grouped under one diagnosis.

As much as possible, each AE or follow-up information will be evaluated to determine:

1. Severity grade (CTCAE Grade 1-5)
2. Duration (start and end dates)
3. Relationship to the study treatment or process – [Reasonable possibility that AE is related: No (unrelated/ not suspected) or Yes (a suspected adverse reaction)]. If yes (suspected) - is the event possibly, probably or definitely related to the investigational treatment?
4. Expectedness to study treatment or process – [Unexpected – if the event severity and/or frequency is not described in the investigator brochure (if applicable) or protocol].
5. Action taken with respect to study or investigational treatment or process (none, dose adjusted, temporarily interrupted, permanently discontinued, unknown, not applicable)
6. Whether medication or therapy taken (no concomitant medication/non-drug therapy, concomitant medication/non-drug therapy)
7. Whether the event is serious

All AEs occurring during the study period are recorded. The clinical course of each event is followed until resolution, stabilization, or until the cause is determined. Serious adverse events (SAEs) ongoing at the end of the study period are followed up to determine the final outcome.

CONFIDENTIAL

This material is the property of the University of Pennsylvania.

8.4 Reporting of Serious Adverse Events (SAEs) and Unanticipated Problems

Reporting period

Adverse events are reported from the time of informed consent until study completion. For this study, study completion is defined as the conclusion of surgery.

Investigator reporting:

Every SAE, regardless of suspected causality (e.g., relationship to study drug(s) or study procedure or disease progression) is reported to the Pharmacovigilance Officer within **24 hours** of learning of its occurrence.

Recurrent episodes, complications, or progression of the initial SAE is reported as the follow-up to the original episode within 24 hours of the investigator receiving the follow-up information. An SAE considered completely unrelated to a previously reported one is reported separately as a new event.

Send the notification (MedWatch or CIOMS form) to the Pharmacovigilance Officer.

New information regarding the SAE is reported as it becomes available and in the same manner that the initial SAE (i.e. MedWatch or CIOMS). The investigator follows the event to resolution or until the event is deemed and documented irreversible, whichever is longer.

Investigator Reporting: Local Reporting Requirements

The investigator reports AEs and SAEs to his/her IRB of record and other local regulatory groups per the local requirements.

8.5 Reporting Serious Adverse Events (SAEs) to the Data Safety Monitoring Committee (DSMC) at the Local PI site

The following are reported to the DSMC:

- All **SAEs** defined as reportable in the protocol.
- All AEs grade 3 or higher within 10 days of knowledge.
- All unexpected deaths within 24 hours of knowledge.
- All other deaths within 30 days of knowledge.

